8.0 Demographics, Baseline Characteristics, Medical History, and Prior/Concomitant Medications

Demographics, baseline or disease characteristics, medical history, and prior and concomitant medications will be summarized for the mITT analysis set overall and by treatment group. Categorical variables will be summarized with the number and percentage of subjects; percentages will be calculated based on the number of non-missing observations. Continuous variables will be summarized with descriptive statistics (number of non missing observations, mean and standard deviation, median, minimum and maximum).

8.1 Demographics and Baseline Characteristics

Continuous demographic variables include age, weight, weight by sex, height, and body mass index (BMI). Categorical demographic variables include sex, ethnicity, race, age (<40, 40 – < 65, \geq 65 years), BMI (< 25 or \geq 25 kg/m²), country (United States or Canada), tobacco user (current, former, never, unknown), and alcohol user (current, former, never, unknown). The variables used for stratification of randomization as described in Section 4.2.2 will be summarized with the number and percentage of subjects.

8.2 Medical History

Medical history data will be coded using the Medical Dictionary for Regulatory Activities (MedDRA). The actual version of the MedDRA coding dictionary will be noted in the

statistical tables and clinical study report. The number and percentage of subjects in each medical history category (by MedDRA system organ class and preferred term) will be summarized overall and by treatment group for the safety analysis set. The system organ class (SOC) will be presented in alphabetical order, and the preferred terms will be presented in alphabetical order within each SOC. Subjects reporting more than one condition/diagnosis will be counted only once in each row (SOC or preferred term).

8.3 MS Disease History

The number and percentage of subjects with each type of MS and number of relapses in the past 5 years (0, 1, 2, 3, \geq 4) will be summarized categorically. The time in months since onset of first symptoms, and time in months since most recent relapse will be summarized continuously with descriptive statistics overall and by treatment group.

8.4 Prior and Concomitant Medications

Prior and concomitant medications will be summarized by generic name. A prior medication is defined as any medication taken prior to the date of the first dose of study drug. A concomitant medication is defined as any medication that started prior to the date of the first dose of study drug and continued to be taken after the first dose of study drug or any medication that started on or after the date of the first dose of study drug, but not after the date of the last dose of study drug plus 24 weeks (168 days). The number and percentage of subjects taking medications will be summarized by generic drug name based on the World Health Organization (WHO) Drug Dictionary for both prior and concomitant medications by treatment group and overall.

The number and percentage of subjects taking MS immunmodulators at Baseline, defined as those taking any MS immunmodulator on the first dose date, will be summarized by generic drug name by treatment group and overall.

8.5 Protocol Deviations and Visit Modifications

The number and percentage of subjects who reported at least one protocol deviation will be summarized by treatment group and overall.

The number and percentage of subjects with in-person partial visits, virtual visits, and missed visits will be summarized by treatment group and overall for each visit. The primary reason for an impact to a visit will be summarized by treatment group and overall for each visit. The denominator will be the number of subjects in that treatment group for the by-treatment summary, or in the entire mITT analysis set for the overall summary.

9.0 Efficacy Analyses

9.1 General Considerations

All efficacy endpoints will be analyzed on mITT analysis set. The primary and secondary efficacy endpoint analyses will be repeated for the RF analysis set and the MMIA set as described in Section 5.1. Additional exploratory analyses will be repeated based on a subset of the population with a pre-defined deficit at baseline where noted.

For all exploratory efficacy analyses other than those related to MRI variables, where a continuous summary by visit is noted, the descriptive statistics based on the observed visit values will be provided by treatment group. The statistics include number of observations, mean, standard deviation, minimum, median, and maximum. The number and percentage will be summarized for categorical variables.

For all efficacy endpoints where change from baseline will be analyzed with an MMRM, the mean at baseline and that visit will be presented, as well as the LS means standard error, and the between group difference, standard error, and 95% confidence interval.

Baseline for efficacy will be defined as the last non-missing observation that is on or before the first dose date.

9.2 Primary Efficacy Analysis

The primary efficacy variable is the ORS at Week 52 and secondary efficacy variables are the ORS at Weeks 12, 24, and 36. The ORS will be summarized continuously as observed (including n, mean, standard deviation, minimum, median and maximum) at each visit.

The frequency and percentage of subjects with each ORS score in the range of -4 to +4 will also be provided by treatment group at each visit. The data will be summarized as observed, i.e., no imputations will be implemented.

The comparisons between the each elezanumab group and placebo for the primary efficacy endpoint ORS at each scheduled visit during the treatment period will be performed using anMMRM. The ORS for each treatment group at scheduled visits and overall will be estimated from the model. The within group LS mean 95% confidence interval, pooled standard deviation, effect size, and 95% confidence interval for the effect size will also be presented by treatment group. The model will include the fixed effects of treatment, visit, the stratification factors of diagnosis of MS (RRMS or rSPMS) and background MS immunotherapy (Yes or No), and the treatment-by-visit interaction, with baseline scores (EDSS, T25FW, 9HPT-D, 9HPT-ND) as covariates. The REPEATED statement will be used for visit with blocks in the covariance matrix identified by subject nested within treatment group. The unstructured covariance structure will be used to estimate the within subject variance-covariance. If the model fails to converge, the first order autoregressive (AR[1]) covariance structure will be substituted. If the model still fails to converge, the compound symmetry (CS) covariance structure will be substituted. Denominator degrees of freedom will be computed using the Kenward-Roger method.

This will be repeated for the RF and MMIA sets.

The posterior probability that each elezanumab group's effect size is greater than 0.1, 0.3, and 0.5 will be presented for the mITT analysis set.

The ORS and corresponding 95% confidence interval based on the MMRM for the mITT analysis set will be plotted at each time point during the treatment period by treatment group.

The post-treatment ORS scores will be summarized continuously as observed.

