4.4 Sample Size Justification

Approximately 165 subjects will be equally randomized 1:1:1 to each treatment group (approximately 55 subjects in each treatment, with at least 20 rSPMS subjects and approximately 35 RRMS subjects). There is limited prior data to estimate the magnitude of effect and variance. This sample size will have approximately 80% power to detect an

effect size (ES) of 0.43 with significance level of 0.1 and overall dropout rate of approximately 10%, using a 1-sided t-test.

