9.4 Other Efficacy Analyses

Change from baseline treatment comparison at each visit will be conducted using an MMRM model including treatment group, visit, treatment-by-visit interaction, and stratification factors as fixed effects, the baseline values associated with the endpoint as covariates. The REPEATED statement will be used for visit with blocks in the covariance matrix identified by subject nested within treatment group. The unstructured covariance structure will be used to estimate the within subject variance-covariance. If the model fails to converge, the first order autoregressive (AR[1]) covariance structure will be substituted. If the model still fails to converge, the compound symmetry (CS) covariance structure will be substituted. Denominator degrees of freedom will be computed using the Kenward-Roger method.

For binary efficacy endpoints, the frequency and percentage will be provided by treatment group unless otherwise noted.

9.4.1**Confirmed Improvement on the EDSS + and its components**

Confirmed 12-week disability improvement on the EDSS + or components of the EDSS + indicates a subject has clinically significant improvement at a visit as well as the next visit for one or more EDSS+ components, or if the next visit is missing, the subsequent visit. Confirmation may include assessments collected in the post-treatment follow-up period. The improvement confirmation must be in the same component of the EDSS +. If a subject has improvement in more than one component of the EDSS +, the subject must have confirmation in at least one of the same components to be considered as having confirmed disability improvement. For example, if a subject has clinically significant improvement in the T25FW at Week 12, the subject must have clinically significant improvement in the same component of the EDSS + at Week 24 (or if Week 24 is missing, Week 36) to be considered to have confirmed improvement.

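### If the unstructured MMRM fails to converge, the fallbacks AR(1) and CS impose one variance on all visits, so the Week 52 standard error would be too small if the spread of the ORS grows over time

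*SAP*

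**What the plan says.** SAP 9.2 sets the first choice for the ORS model: "The unstructured covariance structure will be used to estimate the within subject variance-covariance". The next step is "If the model fails to converge, the first order autoregressive (AR[1]) covariance structure will be substituted". The last step is "If the model still fails to converge, the compound symmetry (CS) covariance structure will be substituted" (quoted from SAP 9.4; SAP 9.2 has the same step). On inference it adds: "Denominator degrees of freedom will be computed using the Kenward-Roger method".

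The same order appears in SAP 9.4 (other change-from-baseline MMRMs), 9.4.11 (lesion MTR) and 9.5 (subgroup model). None of these sections names a structure with a separate variance per visit, or a robust standard error.

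The ORS model has four visits: "The primary efficacy variable is the ORS at Week 52 and secondary efficacy variables are the ORS at Weeks 12, 24, and 36". On size, SAP 4.4 says: "Approximately 165 subjects will be equally randomized 1:1:1 to each treatment group". It acknowledges that prior data on effect and variance are limited. Neither document gives an ORS standard deviation at any visit.

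**The concern.** AR(1) and CS in their standard forms have two parameters: one variance shared by all visits and one correlation. AR(1) also treats visits as equally spaced, although Weeks 12, 24, 36 and 52 are 12, 12 and 16 weeks apart.

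The ORS counts threshold crossings relative to baseline, so it is zero at baseline by construction. It is plausible that subjects move further from zero, in either direction, as time passes. If they do, a shared variance averages the less variable early visits with the more variable last one. The primary comparison is at the last visit, so its standard error would be too small, its interval too narrow and its error rate above nominal. Kenward-Roger adjusts for small samples under the assumed structure. It does not correct that structure.

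**Working it through.** **Plan's own figure.** SAP 4.4 puts the power near 80%. Its inputs are "effect size (ES) of 0.43 with significance level of 0.1 and overall dropout rate of approximately 10%, using a 1-sided t-test". With 55 per arm and 10% dropout, n = 55 × 0.90 = 49.5. Power = Φ(0.43 × √(49.5/2) − 1.2816) = Φ(0.858) = 80.4%; the noncentral t gives 80.2%. The stated power reproduces.

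**Covariance parameters, four visits.** Unstructured: 4 × 5/2 = 10. AR(1) or CS: 2.

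**Formula.** With complete data and treatment-by-visit means, the fallback replaces the Week 52 variance by roughly the average over visits:

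- SE ratio r = √(mean of the four visit variances) / SD at Week 52
- true error of a one-sided 10% test = 1 − Φ(1.2816 r)
- true coverage of a 95% interval = 2Φ(1.96 r) − 1

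Example, SDs 0.8, 0.9, 1.0, 1.1: mean variance = (0.64 + 0.81 + 1.00 + 1.21)/4 = 0.915; r = √0.915/1.1 = 0.87.

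All SD patterns below are assumptions.

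| SD at Weeks 12, 24, 36, 52 | Mean variance | SE ratio | One-sided error | 95% coverage |
|---|---|---|---|---|
| 1, 1, 1, 1 | 1.000 | 1.00 | 10.0% | 95.0% |
| 0.9, 0.95, 1, 1.05 | 0.954 | 0.93 | 11.7% | 93.2% |
| 0.8, 0.9, 1, 1.1 | 0.915 | 0.87 | 13.3% | 91.2% |
| 0.7, 0.85, 1, 1.15 | 0.884 | 0.82 | 14.7% | 89.1% |
| 0.6, 0.8, 1, 1.2 | 0.860 | 0.77 | 16.1% | 87.0% |
| 1.1, 1, 0.9, 0.8 | 0.915 | 1.20 | 6.3% | 98.1% |

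**Simulation check.** REML fits, 400 runs per scenario, 3 × 55 subjects, 10% random monotone dropout, true correlation parameter 0.6 of AR or CS type, no covariates, t with 140 df in place of Kenward-Roger. Results for the AR(1) and CS fallbacks:

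- Flat SD: SE ratio 0.98 to 1.01.
- SD 0.8 to 1.1: ratio 0.85 to 0.88, one-sided error 13.4% to 13.6%, coverage 91.5% to 92.0%.
- SD 0.6 to 1.2: ratio 0.75 to 0.78, error 15.8% to 16.6%, coverage 84.5% to 88.5%.

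With a separate variance per visit and the matching correlation type (ARH(1) or CSH), the ratio was 0.99 to 1.01, error 9.9% to 10.0% and coverage 95.0% to 95.5% in all three patterns. The Monte Carlo standard error of a coverage near 95% is √(0.95 × 0.05/400) = 1.1 percentage points. TOEPH was not simulated, but ARH(1) and CSH are special cases of it.

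**The case against.** A reader might infer that the interval is too narrow whenever the fallback is used. The documents do not support that. They report no ORS spread by visit, and a zero baseline does not establish growth: baseline is not a modelled visit, and by Week 12 the score already carries measurement error from two assessments. The protocol also selects subjects at reduced risk of relapse. With flat spread there is no bias, and with shrinking spread the test is conservative. This objection stands, and the point is conditional because of it.

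A reader might also infer that the primary result is exposed. It hardly is: 10 covariance parameters and about 165 subjects make failure unlikely. Nor is the SAP 9.5 subgroup model a set of small-subset fits; it is one interaction model on the full mITT set. Failure is more plausible in the deficit-subset MMRMs for SDMT, MFIS-5 and low contrast acuity (SAP 9.4.6 to 9.4.8). The table was worked for the ORS, and the documents do not show that spread grows on those scales either.

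The plan also has partial protection. SAP 9.2 reports the observed ORS standard deviation at each visit, so growth would be visible. SAP 9.3.1 repeats the ORS comparison after multiple imputation with an ANCOVA at each visit, which imposes no common variance. That analysis does not cover the deficit subsets.

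What remains is that, should the unstructured fit fail, the SAP moves straight to the most restrictive variance assumption when less restrictive ones exist.

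**Conclusion.** The point holds as a conditional one. It needs two things: the unstructured model fails, and the Week 52 spread exceeds the average over visits. Over the assumed flat-to-growing patterns, the Week 52 SE ratio runs from 1.00 to 0.77, one-sided error from 10.0% to 16.1%, and 95% coverage from 95.0% to 87.0%. The lower end assumes that the SD doubles between Week 12 and Week 52 and should not be read as the expected case. The direction reverses if spread shrinks.

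The unequal gaps are a secondary matter: with complete data the Week 52 standard error depends on the variance, not on the correlation pattern. Severity is low. This is a worthwhile refinement for an unlikely contingency in a Phase 2a proof-of-concept study.

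**What to change.** Amend the fallback sentences in SAP 9.2, 9.4, 9.4.11 and 9.5 as follows.

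- **Three or more post-baseline visits:** unstructured, then heterogeneous Toeplitz (TOEPH), then heterogeneous compound symmetry (CSH), keeping Kenward-Roger throughout.
- **Last resort, only if these also fail:** CS with the empirical (sandwich) standard error and a compatible degrees-of-freedom method, for example between-within, in place of Kenward-Roger. State that the sandwich standard error can itself be too small in small subsets.
- **Two post-baseline visits (lesion MTR and MSIOA, both at Weeks 24 and 52):** TOEPH and CSH have 2 variances + 1 correlation = 3 parameters, the same model as unstructured. Go directly to CS with the robust standard error.

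Cost: a few SAP sentences, with no effect when the unstructured model converges. With four visits TOEPH has 4 + 3 = 7 covariance parameters and CSH has 4 + 1 = 5, against 2 for AR(1) or CS, so the new steps are somewhat more likely to fail themselves. TOEPH still indexes correlation by visit number and so does not address the unequal gaps; CSH makes no spacing assumption.

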9.3 Secondary Efficacy Analyses

Disability improvement on the EDSS + indicates clinically significant improvement on at least 1 of the components of the EDSS + (EDSS, T25FW, 9HPT [either hand]) as defined by the clinically significant change thresholds in Section 4.3.1).

Improvement responder status on the EDSS + and each of its components will be analyzed by time point based on the criteria in Section 4.3.1. No confirmation will be required, i.e., improvement at the analysis time point only is required to be considered a responder.

The analysis will be presented at each time point with the number and percentage of responders, and the 95% confidence interval for the proportion of subjects based on Wald confidence limits, and the odds ratio and corresponding 95% confidence interval based on the logistic regression model including baseline as a covariate and treatment as a main effect. The model for the EDSS + will include the baseline EDSS, baseline T25FW, baseline 9HPT-D, baseline 9HPT-ND as covariates and treatment as a main effect. This will be presented based on the mITT, RF and MMIA analysis sets using non-responder imputation. The logistic regression analysis will be repeated for the mITT analysis set based on the same multiple imputation as detailed in Section 9.3.1.

A summary of the improvement responder status on the EDSS + and each of its components will be presented for the mITT analysis set as observed.

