Confirmed 24-week improvement on the EDSS + or components of the EDSS + indicates a subject has clinically significant improvement at 3 consecutive visits, or if one of the two subsequent visits are missing, subject demonstrates clinically significant improvement at two of the subsequent three visits. Improvement status after confirmed improvement is not considered, i.e., if a subject has disability improvement in one component of the EDSS + at Week 12 and Week 24, then this subject is considered to have 12-week confirmed disability improvement regardless of a Week 36 status of clinically significant worsening, no clinically significant change, or clinically significant improvement.

The 12-week and 24-week confirmed disability improvement response rate will be summarized for the study for the EDSS +, as well as each of the individual components for the mITT, RF, and MMIA analysis sets based on a non-responder imputation. The frequency and percentage will be provided by treatment group. The treatment comparison will be conducted using the logistic regression model adjusted for the stratification factors and baseline scores associated with the endpoint. The proportion of responders, difference in responder rate, and 95% confidence interval for the responder rate based on

Wald confidence limits will be presented based on the univariate summary. The odds ratio, and 95% confidence interval will be derived from the logistic regression model.

The analyses for confirmed disability improvement will be repeated for the RF and MMIA analysis sets as noted those respective sections.

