9.4.11 MRI Parameters

The MRI parameters of interest and analyses are listed in Section [4.3.3](#).

The number and percentage of subjects with active lesions will be summarized for T1 GAD-enhancing lesions and T2 hyperintense lesions (separately). The difference in the proportion between elezanumab and placebo groups with the 95% confidence interval for the difference based on Wald confidence limits will be presented.

The cumulative number of total T1 GAD-enhancing lesions, cumulative number of total T2 hyperintense lesions, cumulative number of post-baseline T1 GAD-enhancing lesions, cumulative number of post-baseline new and enlarging T2-lesions, will be summarized with continuously and analyzed using an analysis of covariance (ANCOVA). The model for the analysis of the cumulative number of total lesions will include treatment, the stratification factors of diagnosis of MS (RRMS or rSPMS) and background MS immunotherapy (Yes or No). For the cumulative number of lesions during the treatment period, only subjects with Baseline, Week 24, and Week 52 MRIs will be included. For the cumulative number of lesions post-baseline, only subjects with Week 24 and Week 52 will be included.

The number of T1 GAD-enhancing lesions at each visit (Baseline, Week 24, Week 52) will be summarized categorically with the number and percent of subjects for the following categories: 0, 1, 2, 3, 4, 5, > 5.

The following endpoints will be analyzed using change or percent change from baseline using an ANCOVA model.

- Change from Baseline in total volumes of T1 GAD-enhancing lesions
- Change from Baseline in total volume of T2 hyperintense lesions
- Percent change from Baseline in whole brain, gray matter (GM), thalamus, white matter (WM) and normal appearing white matter (NAWM) volumes
- Change from Baseline in regional magnetization transfer ratio (MTR) parameters for whole brain, and NAWM, and MTR for T2 lesions

- Change from Baseline in diffusion tensor imaging (DTI) parameters (fractional anisotropy and Apparent Diffusion Coefficient (ADC)) for whole brain, NAWM and T2 hyperintense lesions
- Change from Baseline in cervical spinal cord area, volume and number of lesions
- Change from Baseline in regional MTR for cervical spinal cord lesions
- Change from baseline in DTI parameters (fractional anisotropy and ADC) for cervical spinal cord

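### Wald limits for the single-arm responder rates under-cover, and collapse at zero responders, if a true rate is below about 5%; Wilson limits would be better (minor)

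*SAP*

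**What the plan says.** SAP 9.3 tabulates improvement responders on the EDSS+ and on each component at each visit, with a "95% confidence interval for the proportion of subjects based on Wald confidence limits". The treatment comparison is separate: "the odds ratio and corresponding 95% confidence interval based on the logistic regression model including baseline as a covariate". On missing data it says: "This will be presented based on the mITT, RF and MMIA analysis sets using non-responder imputation".

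SAP 9.4.1 reports 12- and 24-week confirmed improvement, for the EDSS+ and each component, under the same non-responder rule. There, "Wald confidence limits will be presented based on the univariate summary"; these limits are for the responder rate. The between-arm difference in rate is reported without an interval, and the comparison is again a logistic odds ratio.

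Three other sections use Wald limits differently:
- SAP 9.4.2 (progression) uses them for single-arm rates, but on the multiply imputed data of 9.3.1 (30 datasets).
- SAP 9.4.6 (SDMT gain of at least 4 points) uses them for the difference from placebo.
- SAP 9.4.11 (active T1 and T2 lesions) also uses them only for the difference: "95% confidence interval for the difference based on Wald confidence limits will be presented". No single-arm interval for lesion activity is specified.

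SAP 4.4 sets the size: "Approximately 165 subjects will be equally randomized 1:1:1 to each treatment group (approximately 55 subjects in each treatment". Neither document gives an expected responder or lesion-activity rate, a small-sample alternative to Wald, or a rule for zero counts.

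**The concern.** The Wald interval takes its width from the observed proportion. When few subjects respond, the estimated standard error is too small; when none respond, it is zero. A printed interval of [0, 0], or one that runs below zero, misstates what about 55 subjects can show: sparse data look like a precise finding of no response.

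Several features of the plan make low rates possible.
- Inclusion criterion 10 (protocol 5.1) admits a subject on EDSS alone, with no walking or hand deficit required, so some subjects have little room for a 20% gain on those tests.
- Each component, including each hand, is reported separately.
- Confirmation must be in the same component, and the 24-week version needs three consecutive visits, or two of the following three if one is missing.
- Counting missing data as non-response lowers the observed rate further, and the SAP acknowledges missed visits during the pandemic.

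What is at stake is the accuracy of the error bars in these descriptive tables.

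**Working it through.** **Inputs.** Planned size is 55 per arm (SAP 4.4). Under non-responder imputation the mITT denominator stays near 55. True rates are not given, so a range from 1% to 50% is assumed.

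**The plan's own figure.** SAP 4.4 gives these inputs: "effect size (ES) of 0.43 with significance level of 0.1 and overall dropout rate of approximately 10%, using a 1-sided t-test". The power it states for them is about 80%. Evaluable per arm: 55 × 0.90 = 49.5. Noncentrality: 0.43 × √(49.5/2) = 2.139. Normal approximation: Φ(2.139 − 1.282) = 80.5%; the noncentral t gives 80.2%. The stated power reproduces, so 55 per arm is a sound basis for what follows.

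**Wald limits at low counts, n = 55.** Formula: p̂ ± 1.96 √(p̂(1 − p̂)/n).

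| Responders | Wald | Wilson |
|---|---|---|
| 0 | 0 to 0 | 0 to 6.5% |
| 1 | −1.7% to 5.3% | 0.3% to 9.6% |
| 2 | −1.3% to 8.6% | 1.0% to 12.3% |
| 3 | −0.5% to 11.5% | 1.9% to 14.9% |

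**Exact coverage, single proportion.** Coverage is the sum of the binomial probabilities of every count whose interval contains the true rate p. For Wald at p = 2%, the count 0 misses, with probability 0.98^55 = 32.9%. Counts 1 to 5 cover and counts of 6 or more miss (0.1%). Coverage is therefore 100 − 32.9 − 0.1 = 67.0%. For Wilson at the same rate, counts 0 to 3 cover: 32.9 + 37.0 + 20.4 + 7.3 = 97.6%.

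| True rate | Wald | Wilson | Chance of [0, 0] under Wald |
|---|---|---|---|
| 1% | 42.4% | 89.5% | 57.5% |
| 2% | 67.0% | 97.6% | 32.9% |
| 3% | 81.1% | 97.6% | 18.7% |
| 5% | 93.5% | 94.4% | 6.0% |
| 10% | 91.5% | 93.4% | 0.3% |
| 20% | 92.4% | 93.9% | about 0 |
| 30% | 94.3% | 96.2% | about 0 |
| 50% | 94.2% | 94.2% | about 0 |

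Wald coverage moves in a saw-tooth, so 5% is not a clean boundary. At 6% it drops to 84.5%, because a count of 1 has an upper limit of 5.3% and now misses too. Averages by band are steadier: 76.9% for true rates of 1% to 5% (Wilson 95.8%), 89.2% for 5% to 10%, 92.6% for 10% to 20%, and about 94% above that.

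The RF and MMIA sets can be no larger than mITT. At an assumed n = 40, Wald covers 55% at a rate of 2% and 87% at 5%.

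**Exact coverage, difference of two proportions, 55 vs 55** (relevant to 9.4.6 and 9.4.11).

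| True rates | Wald | Newcombe | Chance of zero events in both arms |
|---|---|---|---|
| 1% vs 1% | 99.7% | about 100% | 33.1% |
| 2% vs 2% | 98.3% | 99.7% | 10.8% |
| 1% vs 3% | 80.9% | 99.3% | 10.8% |
| 2% vs 5% | 92.9% | 98.6% | 2.0% |
| 5% vs 5% | 94.2% | 97.6% | 0.4% |
| 5% vs 10% | 93.5% | 96.1% | about 0 |
| 10% vs 20% | 94.5% | 95.4% | about 0 |

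The last column is [(1 − p1)(1 − p2)]^55. Once both rates reach 5%, Wald coverage for the difference averages 94.5% over the grid examined.

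**The case against.** The strongest reply is that this hardly matters. The endpoint that SAP 9.3 makes secondary is unconfirmed improvement on any component at a single visit, the least rare definition in the plan. If its rate is 20% to 50% (an assumption), Wald covers about 92% to 94.5% and a zero-width interval is practically impossible. The single-arm limits carry no decision rule. Comparisons rest on odds ratios, the primary ORS analysis uses no proportion interval, and the count printed beside each interval shows a reader that 0 of 55 responded. All of this stands, and it sets the priority.

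It does not remove the point. The same rule governs the single-component and confirmed rates, where low counts are plausible. In an arm with no responders, ordinary logistic regression has no finite treatment estimate and the SAP names no fallback. The single-arm interval is then the main usable statement of uncertainty.

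A reader might infer that the active-lesion tables suffer the same collapse, because enhancing lesions may be rare in subjects chosen for low relapse risk. The SAP does not support that. Lesion activity and SDMT response receive only a difference interval, to which the single-arm coverages do not apply. Zero width there requires no events, or all events, in both arms, and under-coverage arises mainly when the rates differ and at least one is about 2% or less.

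**Conclusion.** The concern holds for the single-arm rates in SAP 9.3 and 9.4.1. If a true rate is below about 5%, the nominal 95% Wald limits can cover far less (42% at 1%, 67% at 2%, 81% at 3%), may run below zero, and may have no width. Coverage remains a few points low, at about 92%, for rates of 10% to 20%. These figures assume 55 independent subjects per arm.

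It is tempting to conclude that many of the planned intervals would fail. The documents cannot support that, because they give no expected rates and the result depends wholly on the rate. The supportable statement is conditional: those single-arm intervals whose true rate is low will be wrong, and single-component and confirmed improvement are the likeliest places. Priority is minor.

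**What to change.** - **SAP 9.3 and 9.4.1:** replace Wald with Wilson limits for the single-arm rates. Zero responders then gives 0 to 6.5% at 0/55. The cost is one option in the SAS frequency procedure and a few words; intervals at common rates barely change.
- **SAP 9.4.6 and 9.4.11:** use Newcombe (Wilson-based) limits for the differences. The cost is similar. The gain is small, and the downside is some over-coverage at very low rates (99.3% at 1% vs 3%).
- **SAP 9.4.2:** a single-dataset option does not give a pooled interval over 30 imputations. Specify an interval suited to pooling, such as Rubin's rules on the logit scale or a Wilson interval adapted to multiple imputation. The logit needs at least one event and one non-event in every imputed dataset, so the adapted Wilson form is safer at very low counts. This takes modest extra programming.

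The MMRM, the logistic models and the sample size are unaffected.
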